3.1 Study Design

This is an observational, prospective, multicenter study in adult patients with T2DM diagnosis who have made the decision, along with their treating physician, to begin treatment with alogliptin or alogliptin FDCs.

This is a non-interventional study as defined in the Directive 2001/20/EC (The European Parliament and the Council of the European Union 2001) and will follow the Good Pharmacoepidemiology Practices (GPP) guidelines (Epstein 2005). This means that:

- The assignment of a patient to a particular therapeutic strategy is not decided in advance by the study protocol but falls within current practice.
- No additional diagnostic or monitoring procedures shall be applied to the patients.
- Epidemiological methods shall be used for the analysis of collected data.
- The prescription of alogliptin or alogliptin FDCs is clearly separated from the decision to include the patient in the study.

The purpose of this study is to observe alogliptin and alogliptin FDCs utilization patterns, as well as clinical response to treatment with alogliptin or alogliptin FDCs, in standard clinical practice. No investigational product will be administered in this study.

The observational study will include approximate 1199 patients with T2DM treated with alogliptin or alogliptin FDCs in approximately 40 sites.

The planned maximum duration of this study per patient will be 6 months or up to loss to follow-up or death, whichever occurs first. China Guideline For Type 2 Diabetes recommends HbA1c as the gold standard for blood glucose monitoring. The guideline recommends HbA1c should be tested every 3 months when new treatment regimen is initiated, and when HbA1c is in the treatment target, HbA1c test can be followed every 6 months. In this study, since the treatment of all the patients recruited are with alogliptin initiated, according to the guideline and the standard clinical practice, HbA1c is normally tested every 3 months before HbA1c hits the treatment target and keep stable. So in this study, Patients will attend a baseline visit followed by visits approximately at Month 3 and 6.

Patients will not be asked to travel to the site only for the purpose of this study; the study visits will be performed during regular doctor's appointments.

The data collected for this study are detailed in Section 6, and the Data Collection Schedule is provided in Table 12-1.

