## **8.2. Data Handling Conventions**

### **8.2.1. Premature Withdrawal and Missing Data**

When a patient withdraws from the study, the reason(s) for withdrawal shall be recorded by the investigator on the relevant page of the electronic case report form (eCRF). Patients lost to follow-up will be contacted by the site in an attempt to determine the reason for study withdrawal. A maximum of 3 telephone call attempts should be documented on different days. Patients who withdraw from the study will not be replaced.

No imputation will be used for Missing data.

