### **8.2.2. Definition of Baseline and Change from Baseline**

In this study, patients will attend a baseline visit followed by visits approximately at Month 3 and 6. Data collected at the baseline visit will be regarded as baseline. For HbA1c assessment, the latest HbA1c value available before the starts of alogliptin or alogliptin FDC (but within 3 months before the first dosage) will be considered the baseline value.

The change from baseline will be calculated by subtracting the baseline values from the individual post-baseline values. If either the baseline or post-baseline value is missing, the change from baseline is set to missing as well.

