### **8.4.2. Secondary Efficacy Analyses**

The secondary HbA1c or fasting blood glucose outcomes (HbA1c clinical response rates) will be summarized by treatment as descriptive statistics and incidence rates.

If multiple HbA1c levels are available, then the assessment closest to the visit time point will be used. Clinical response rates: incidence rates of responders. The following definitions of response will be used: (1) HbA1c level reduction to the goals of <7.0%. (2) HbA1c reduction >0.3% with no tolerability findings (hypoglycemic event, or weight gain  $\geq 5\%$ ).

- HbA1c level change from baseline in subgroups with different clinical characteristics. It is proposed to use multifactorial regression model to determine factors related to effect of alogliptin and its FDCs on HbA1c level dynamics. Change from baseline in HbA1c level on alogliptin or its FDCs therapy (V3) in subgroups with different clinical characteristics will be summarized using relevant descriptive statistics and analyzed using Multiple Linear Regression with following predictors: prior therapy of DM, sex, age, cardiovascular risk group, therapy type (monotherapy or combined therapy), baseline BMI, initial glycemic control.

In addition, change from baseline in HbA1c level will be assessed and evaluated using mixed model repeated measures (MMRM) methodology. The multiple visits for each patient will be incorporated as repeated measures within each patient. Visit will be treated as a categorical predictor and baseline HbA1c level will be included as a covariate. An appropriate covariance structure will be selected to provide estimates (Least Square Means) of change from Baseline and to perform statistical analysis at Visit 3. If the unstructured covariance matrix results in a lack of convergence, the heterogeneous Toeplitz covariance structure, followed by the heterogeneous autoregressive covariance structure, followed by compound symmetry will be used. The dose-response trend hypothesis test will be conducted using the appropriate contrast statement for a linear (ordinal dose) trend. In addition, Least Squares Means, the associated standard errors and 95% confidence intervals will be displayed by each individual dose group.

[figure not shown]
- Proportion (%) of patients with diabetes mellitus type 2 whose HbA1c<7.0% will be described and presented in summary tables using absolute frequencies and percentages as well as 95% confidence intervals;

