## **9. Impact on Analysis Due to Study Termination**

Due to Takeda's decision, Alogliptin 5009 study need to be early-terminated. The impact will include below three aspects:

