## **9.3. Impact of Limited Visit**

The study termination will lead to missing visit of V2 or V3, and efficacy results might not be obvious.

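### The Visit 3 factor effects come from a regression limited to patients with a Month 6 HbA1c; fitting the same predictors in the planned repeated-measures model would recover some precision at little cost.

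*SAP*

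**What the plan says.** SAP 4.2 lists HbA1c change in subgroups with different clinical characteristics as a secondary endpoint at V3. SAP 8.4.2 gives its analysis: "Change from baseline in HbA1c level on alogliptin or its FDCs therapy (V3) in subgroups with different clinical characteristics will be summarized" descriptively and then "analyzed using Multiple Linear Regression with following predictors: prior therapy of DM, sex, age, cardiovascular risk group", followed by therapy type, baseline BMI and initial glycemic control. That makes seven predictors and one outcome per patient. Protocol 7.8.2 has the same model.

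Two rules fix who enters it. SAP 8.2.1: "No imputation will be used for Missing data". SAP 8.2.2: "If either the baseline or post-baseline value is missing, the change from baseline is set to missing as well".

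SAP 8.4.2 also plans two repeated-measures analyses of HbA1c change. The MMRM in the same bullet names visit and baseline HbA1c as terms, asks for V3 estimates, a dose trend contrast and dose-group least squares means, and gives a sequence of fallback covariance structures. A later bullet plans a repeated-measures mixed model over V1, V2 and V3 with clinical characteristics as factors. It does not list the characteristics and does not mention an interaction with visit.

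SAP section 9 was written after the decision to stop: "Due to Takeda's decision, Alogliptin 5009 study need to be early-terminated". Section 9.3 adds: "The study termination will lead to missing visit of V2 or V3, and efficacy results might not be obvious". Nothing in section 9 changes the regression.

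**The concern.** A patient with a Month 3 HbA1c but no Month 6 HbA1c contributes nothing to the V3 regression, although the Month 3 value helps predict the missing one. In a study with enrolment well below plan, the analysis of which patients respond best at Month 6 then rests on a smaller data set than it has to.

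The repeated-measures models do not fill the gap as written. The MMRM gives V3 estimates but no effects of the clinical factors. The over-time mixed model has clinical factors but is not specified to give their effects at V3. The SAP does not say which model supplies the reported V3 factor effects.

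Precision is at stake first. Validity comes into it only if the absence of a V3 value is related to the Month 3 result. Protocol 3.1 leaves some room for that, since it notes that "when HbA1c is in the treatment target, HbA1c test can be followed every 6 months" and the study makes no measurements of its own.

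**Working it through.** **1. The plan's own figure.** Inputs from SAP section 6: SD 0.65, correlation 0.35, half-width 0.05, two-sided alpha 0.05, conditional width probability 0.9, dropout 25%.

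- SD of the paired difference = √(2 × 0.65² × (1 − 0.35)) = √0.54925 = 0.741.
- The exact calculation returns 899 pairs with probability 0.904, as stated. All 18 rows of the table reproduce.
- Enrolment: 899 / 0.75 = 1198.7, so 1199, as stated.

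These figures describe the precision of the overall mean change. No stated figure covers the factor effects, so nothing below contradicts a number in the plan.

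**2. Precision of a V3 factor effect.** Suppose Month 3 is seen in all the patients considered and V3 in a fraction f of them, lost at random. Let r be the correlation of the Month 3 and Month 6 residuals after baseline adjustment. In large samples:

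Var(repeated measures with factor-by-visit) / Var(V3-only regression) = 1 − r²(1 − f)

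The SD cancels. Neither f nor r is in the documents. Assumptions: f = 0.75 (loss equal to the planned 25% dropout) and f = 0.50; raw Month 3 to Month 6 HbA1c correlation 0.5 to 0.8; the plan's 0.35 for baseline with each follow-up visit; equal SD at all visits.

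Because baseline HbA1c is adjusted for, r is the partial correlation:

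- raw 0.5: r = (0.5 − 0.35²)/(1 − 0.35²) = 0.3775/0.8775 = 0.430, r² = 0.185
- raw 0.8: r = (0.8 − 0.1225)/0.8775 = 0.772, r² = 0.596

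| Raw correlation | V3 lost | Variance ratio | SE ratio | SE reduction |
|---|---|---|---|---|
| 0.5 | 25% | 1 − 0.185 × 0.25 = 0.954 | 0.977 | 2.3% |
| 0.5 | 50% | 1 − 0.185 × 0.50 = 0.907 | 0.953 | 4.7% |
| 0.8 | 25% | 1 − 0.596 × 0.25 = 0.851 | 0.922 | 7.8% |
| 0.8 | 50% | 1 − 0.596 × 0.50 = 0.702 | 0.838 | 16.2% |

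The gain is thus about 2 to 16% in standard error. In patient numbers it equals 1/0.954 = 1.05 to 1/0.702 = 1.42 times as many patients with V3.

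**3. Bias.** Simulation with 400 patients, one binary factor, SD 0.65 and a true V3 effect of −0.20; the missingness patterns are assumed.

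| What missing V3 depends on | Bias of V3-only regression |
|---|---|
| Nothing, or the factor only | about 0 |
| Month 3 HbA1c, equally in both factor levels | +0.01 to +0.03 (toward zero) |
| Month 3 HbA1c, in one factor level only (deliberately strong) | −0.11 to −0.27 (away from zero) |

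The repeated-measures estimate stayed within about 0.005 of the true value throughout. These patterns all satisfy its assumption that V3 is missing at random given Month 3.

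**The case against.** The strongest reply is that the plan already uses the Month 3 data. It does: a reader might infer that these values are thrown away, and that would be wrong, because both repeated-measures analyses in SAP 8.4.2 include them. The over-time mixed model even has clinical characteristics as factors, and nothing in the SAP rules out a visit interaction. What remains is a gap in specification. No model is stated to give V3 factor effects from all visits.

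A reader might also infer that the V3 regression is biased, and biased toward zero. The documents do not support this. The documented reason for missing V3 is a sponsor decision, which is close to a cut-off by enrolment date and gives about zero bias. The clause on six-monthly testing stands beside a statement in protocol 3.1 that testing is normally three-monthly until the target is reached and stable, which is the basis for the Month 3 and Month 6 visits. No retest rates are given. Step 3 also shows that the direction is not fixed.

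Finally, the endpoint is secondary and descriptive, with no formal significance testing, and the precision gain at the low end is slight. That is fair, and it limits the weight of the point. Patients with neither V2 nor V3 add nothing under either model, and their number is not given.

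**Conclusion.** The point holds as a cheap improvement. As specified, V3 factor effects come from a complete-case regression in a study whose SAP says "The study termination will lead to missing visit of V2 or V3". Using Month 3 values would lower the standard error by about 2 to 16%, given a Month 3 to Month 6 HbA1c correlation of 0.5 to 0.8 and random loss of V3 in 25 to 50% of patients who have Month 3. Actual enrolment, V3 availability and that correlation are not in the documents.

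Bias is a conditional risk. It is negligible if the cut-off is purely administrative and arises only if missing V3 depends on the Month 3 result; its direction depends on whether that dependence differs by factor level. The primary endpoint's sample size calculation is unaffected.

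**What to change.** Before database lock, state in SAP 8.4.2 that the V3 factor effects come from the repeated-measures model of change at V2 and V3, with:

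- visit;
- baseline HbA1c by visit, serving as initial glycemic control so that baseline glycemia is not entered twice;
- the other six named predictors, each by visit;
- unstructured covariance, with the fallback sequence already given there.

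Report the V3 coefficients with 95% confidence intervals, and the numbers of patients with V2 only, V3 only, both and neither. Keep the V3-only regression as the sensitivity analysis. Protocol 7.8.2 names the same regression, so record the change as a departure from it.

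The cost is SAP wording and one model, with no new data. The downside is more parameters in a reduced sample, and reliance on V3 being missing at random given Month 3, baseline and the predictors.

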6.1.2 Demographic Data and Medical History

Patient demographic data will include date of birth (if allowed by local regulations), sex, race, ethnicity, height, and body weight.

Medical history will include general medical history (including medications, co-morbidities, and hospitalizations), as well as specific T2DM history (including date of diagnosis and previous treatments received).

Demographic data and medical history will be obtained from medical records and as shown in the Data Collection Schedule (Table 12-1).

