7.4 Baseline Covariates

The following baseline covariates will be used:

- Age, sex, race, ethnicity, vital signs, body weight, height, and body mass index
- T2DM history: time from date of first diagnosis to first alogliptin use, number of different previous diabetic treatments, percentage of patients with each previous diabetic treatment (eg, metformin, sulfonylurea, thiazolidinediones)
- Medical history: medications, co-morbidities, hospitalizations
- Laboratory evaluations, including HbA1c, fasting blood glucose
- Geographical region/country

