7.8.2 Secondary Analyses

The secondary HbA1c or fasting blood glucose outcomes (HbA1c clinical response rates) will be summarized as descriptive statistics and incidence rates.

- HbA1c level change from baseline in subgroups with different clinical characteristics. It is proposed to use multifactorial regression model to determine factors related to effect of alogliptin and its FDCs on glycosylated hemoglobin (HbA1c) level dynamics. Change from baseline in glycosylated hemoglobin (HbA1c) level on alogliptin or its FDCs therapy (V3) in subgroups with different clinical characteristics will be summarized using relevant descriptive statistics and analyzed using Multiple Linear Regression with following predictors: prior therapy of DM, sex, age, cardiovascular risk group, therapy type (monotherapy or combined therapy), baseline BMI, initial glycemic control.

[figure not shown]
In addition, change from baseline in glycosylated hemoglobin (HbA1c) level will be assessed and evaluated using Mixed model repeated measures (MMRM) methodology. The multiple visits for each patient will be incorporated as repeated measures within each patient. Visit will be treated as a categorical predictor and baseline glycosylated hemoglobin (HbA1c) level will be included as a covariate. An appropriate covariance structure will be selected to provide estimates (Least Square Means) of change from Baseline and to perform statistical analysis at Visit 3. The dose-response trend hypothesis test will be conducted using the appropriate contrast statement for a linear (ordinal dose) trend. In addition, Least Squares Means, the associated standard errors and 95% confidence intervals will be displayed by each individual dose group.

- Proportion (%) of patients with diabetes mellitus type 2 whose HbA1c < 7.0% (V3) will be described and presented in summary tables using absolute frequencies and percentages as well as 95% confidence intervals;
- Proportion (%) of patients with diabetes mellitus type 2 who decrease in HbA1c \geq 0.3% over time (V3) will be described and presented in summary tables using absolute frequencies and percentages as well as 95% confidence intervals;

- Change from baseline in fasting plasma glucose level on alogliptin or its FDCs therapy over time (V1-V2-V3) will be summarized using relevant descriptive statistics and analyzed with mixed model with repeated measures using clinical characteristics as independent factors;

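### The regression meant to find factors related to HbA1c response leaves out diabetes duration, so the age, prior-therapy and therapy-type coefficients may carry part of its effect

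*SAP*

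**What the plan says.** SAP 8.4.2 proposes a "multifactorial regression model to determine factors related to effect of alogliptin and its FDCs on HbA1c level dynamics". For change at visit 3 it is a multiple linear regression with the "following predictors: prior therapy of DM, sex, age, cardiovascular risk group, therapy type (monotherapy or combined therapy), baseline BMI, initial glycemic control". Protocol 7.8.2 names the same seven predictors. Neither document includes diabetes duration or says why it is left out.

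Protocol 7.4 opens with "The following baseline covariates will be used" and lists, among others, "time from date of first diagnosis to first alogliptin use" and "Geographical region/country". It does not say in which analysis. Protocol 7.6 and 7.7 refer back to that list for subgroups, and SAP 7.2 repeats it as a set of optional subgroup variables.

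The data exist. Protocol 6.1.2 collects the date of diagnosis, and the data collection schedule (Table 12-1) collects the alogliptin start date at baseline.

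SAP 8.4.2 also plans repeated-measures models of HbA1c and fasting glucose over the three visits, adjusted for clinical characteristics that are not named.

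**The concern.** Protocol 3.1.1 gives learning which patients benefit most as one reason for the study. The seven-predictor regression is the only multivariable model with a named set of patient characteristics for that question.

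Patients with longer-standing diabetes will plausibly be older, have had more previous treatment and be on combined therapy more often. If duration is also related to the HbA1c change, a model without it assigns part of that relation to age, prior therapy or therapy type. The report could then name one of these as the factor that marks good or poor responders when duration accounts for some of the difference. A larger sample does not remove this kind of error, and reporting coefficients without tests does not remove it either.

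**Working it through.** **1. The plan's own figure.** The documents size the study for the whole-cohort mean change and give no figure for the regression. The inputs, from Protocol 7.5 and SAP 6, are SD 0.65, correlation 0.35, half-width 0.05, two-sided alpha 0.05 and conditional probability of width 0.90.

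- SD of the change = 0.65 × √(2 × (1 − 0.35)) = 0.741.
- The exact conditional calculation gives 899 pairs, with probability of width 0.904, as stated.
- With 25% dropout, 899 / 0.75 = 1198.7, so 1199, as stated.

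These figures do not depend on the regression.

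**2. Form of the bias.** For a two-group predictor, bias = (effect of duration per year, given the other predictors) × (difference in mean duration between the groups that remains after the other predictors). If either factor is zero, the bias is zero.

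**3. Size under assumptions.** Neither factor is in the documents. Assume 0.01 to 0.03 HbA1c points per year and a remaining difference of 5 years.

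- Low end: 0.01 × 5 = 0.05.
- High end: 0.03 × 5 = 0.15.
- If the other predictors explained half of that difference, leaving 2.5 years, the range would be 0.025 to 0.075.

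A second set of assumptions works in SD units. With an effect of 0.05 to 0.20 HbA1c points per SD of duration and groups that differ by 0.3 to 0.8 SD, the bias runs from 0.05 × 0.3 = 0.015 to 0.20 × 0.8 = 0.16.

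**4. Yardstick.** The relevant comparison is the precision of a two-group coefficient. With equal groups (assumed), and ignoring both the variance that the model explains and the correlation among predictors, half-width = 1.96 × 2 × 0.741 / √n.

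| n | Half-width | 0.05 to 0.15 as a multiple |
|---|---|---|
| 899 | 0.097 | 0.5 to 1.5 |
| 300 | 0.168 | 0.3 to 0.9 |
| 100 | 0.290 | 0.2 to 0.5 |

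The rows for 300 and 100 are illustrations. SAP 9.1 says that enrolment fell far short of plan but gives no number.

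**5. Cost in precision.** Take the seven predictors as one term each and add one term for duration. The degrees of freedom alone raise a standard error by √((n − 8)/(n − 9)):

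- n = 899: √(891/890) = 1.0006, or 0.06%.
- n = 100: √(92/91) = 1.005, or 0.5%.

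Correlation costs more. If the added term explains 9% of what varies in a predictor after the others, its standard error rises by 1/√0.91 = 1.05. If it explains 25%, the factor is 1/√0.75 = 1.15. With the degrees of freedom included, the rise at n = 899 is about 5% to 16%.

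**The case against.** The Protocol 7.4 list is not a specification of this model. Protocol 7.6, Protocol 7.7 and SAP 7.2 tie it to subgroups, and much else on it is also absent from the regression, such as race, vital signs, fasting glucose and hospitalisations. A reader might infer that the sponsor broke a commitment. The documents do not support that: the omission is an unexplained gap. This part of the objection stands.

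A reader might also infer that the coefficients are in fact confounded. No section gives an association of duration with any predictor or with HbA1c change, so only a possibility can be claimed. Age, initial glycemic control and the other predictors may already account for much of the difference in duration. This stands too, and it is why the size rests on assumptions.

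The analysis is secondary, with no hypothesis (SAP 5) and no formal testing (SAP 8.1). An unadjusted coefficient still describes which patients had larger changes. That is true, but it answers only part of the point: the model's stated purpose is to determine factors, and a coefficient that mixes two characteristics serves that purpose poorly.

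The repeated-measures models may include duration, since their covariates are not named. The omission is therefore certain only for the linear regression. Subgroup summaries by duration are allowed, but they do not adjust the regression.

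Region is tempting as a second omission of equal weight, because Protocol 1 says that the products studied depend on what is available in China and Hong Kong. The model's predictor, however, is monotherapy versus combined therapy, not product. No section links region to that split, to age or to prior therapy. The number of patients per region is not given, and after early termination a region term may be barely estimable.

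**Conclusion.** The point holds for duration, as a specification gap in a secondary analysis. The model omits, without a reason, a listed and collected baseline variable that plausibly tracks three of its seven predictors. The coefficients for age, prior therapy and therapy type may therefore carry part of the effect of duration.

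Under the assumed 0.01 to 0.03 points per year and 5 remaining years, the bias is comparable with the sampling error of a two-group contrast at the planned 899 pairs. At the smaller numbers that SAP 9.1 implies, the same bias would be a smaller share of the uncertainty. Nothing in the documents fixes its size, and it may be zero.

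A reader might set 0.05 to 0.15 against the planned half-width of 0.05 and conclude that the bias is one to three times the study's precision. That comparison is not valid, because 0.05 belongs to the mean change of the whole cohort and not to a regression coefficient.

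For region the documents support only a conditional suggestion. The primary analysis and the sample size are untouched.

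**What to change.** Before database lock, add time from diagnosis to first alogliptin use, continuous in years, to the predictor list in SAP 8.4.2 and Protocol 7.8.2, or state why it is left out. Add region only if both China and Hong Kong have enough patients to estimate it. Name the clinical characteristics used in the repeated-measures models, and describe all coefficients as associations.

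The change takes one line in each document and one degree of freedom, plus the loss of precision shown above for predictors correlated with duration. SAP 8.2.1 plans no imputation, so patients with an unknown diagnosis date would drop out of the model, and their number should be reported. No new data collection is needed. Protocol 10.2.1 requires ethics committee approval for changes that are not merely logistical or administrative, so the protocol edit may need an amendment.

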## 6. SAMPLE SIZE CONSIDERATION

[figure not shown]
Sample size was calculated for the primary endpoint of the study: to evaluate the effect of Alogliptin or its FDCs on glycosylated hemoglobin (HbA1c) level in patients with diabetes mellitus type 2 (V3). Sample size was calculated using SAS 9.3 proc power procedure (power for Confidence Interval for Paired Mean Difference as for accuracy of parameter estimation) for following parameters (fixed scenario elements):

Fixed Scenario Elements	
Distribution	Normal
Method	Exact
Correlation	0.35
Nominal Prob(Width)	0.9
Number of Sides	2
Alpha	0.05
Prob Type	Conditional

Standard deviation was assessed based on S. Del Prato et al study and was considered to be at most 0.70% (for glycosylated hemoglobin level dynamics). To determine required number of patients values from 0.60% to 0.70% were taken. Desired half-width for parameter estimation was set as range between 0.05 – 0.1. Following required number of pairs were calculated:

Computed N Pairs				
Index	Half-Width	Std Dev	Actual Prob(Width)	N Pairs
1	0.05	0.60	0.904	770
2	0.05	0.65	0.904	899

3	0.05	0.70	0.900	1037
4	0.06	0.60	0.904	542
5	0.06	0.65	0.903	632
6	0.06	0.70	0.903	729
7	0.07	0.60	0.906	404
8	0.07	0.65	0.902	470
9	0.07	0.70	0.904	542
10	0.08	0.60	0.902	313
11	0.08	0.65	0.907	365
12	0.08	0.70	0.905	420
13	0.09	0.60	0.905	251
14	0.09	0.65	0.906	292
15	0.09	0.70	0.907	336
16	0.10	0.60	0.904	206
17	0.10	0.65	0.902	239
18	0.10	0.70	0.904	275

For the worst-case scenario of half-width as 0.05, if Std Dev is 0.65, the required number of pairs is 899. Taking into account a possible dropout of 25%, to reach study objectives in regard to this endpoint, it is recommended to enroll at least 1199. If taking Std Dev as 0.60 or 0.70, the required number of pairs is from 770 or 1037. Taking into account a possible dropout of 25%, it is recommended to enroll at least 1027 or 1383 patients into the study.

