## **8.4. Efficacy Analyses**

### **8.4.1. Primary Efficacy Analyses**

Change from baseline in HbA1c level on alogliptin or its FDCs therapy will be summarized as descriptive statistics.

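### The secondary HbA1c MMRM names no baseline-by-visit term and no evaluation point for LS means, so its Visit 3 estimate is biased if baseline slopes differ by visit and Month 6 missingness is selective

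*SAP*

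**What the plan says.** SAP 8.4.2 adds a mixed model for repeated measures to the regression analysis of HbA1c change. The fixed effects are described in one sentence: "Visit will be treated as a categorical predictor and baseline HbA1c level will be included as a covariate". Protocol 7.8.2 has the same two terms: "Visit will be treated as a categorical predictor and baseline glycosylated hemoglobin (HbA1c) level will be included as a covariate". Neither document names a product term between them, and neither says at which baseline value the LS means are computed. The stated purpose is "to provide estimates (Least Square Means) of change from Baseline and to perform statistical analysis at Visit 3". The covariance gets more detail: a sequence of simpler structures applies "If the unstructured covariance matrix results in a lack of convergence".

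The primary analysis is separate (SAP 8.4.1): "Change from baseline in HbA1c level on alogliptin or its FDCs therapy will be summarized as descriptive statistics". SAP 8.2.1 rules out imputation.

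On missing visits, SAP 6 allows for 25% dropout and SAP 9.3 adds: "The study termination will lead to missing visit of V2 or V3". Protocol 3.1 describes three-monthly testing after a new regimen and then says: "when HbA1c is in the treatment target, HbA1c test can be followed every 6 months".

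**The concern.** With main effects only, one slope of change on baseline is fitted to both visits. If every patient had both values this would do no harm, because an LS mean at the mean baseline would not depend on the slope. When Month 6 values are missing selectively, the patients still observed have a different mean baseline from the whole group. The model then has to move the observed Month 6 mean back to the whole-group baseline along a slope partly learned at Month 3. If that slope is wrong for Month 6, the Visit 3 LS mean is wrong too.

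The primary analysis is an observed-case summary without imputation, so this MMRM is the plan's main Visit 3 estimate able to adjust for selective loss. It should make that adjustment with the right slope and at the right baseline value.

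**Working it through.** **1. The plan's own figure.** SAP 6 states: "For the worst-case scenario of half-width as 0.05, if Std Dev is 0.65, the required number of pairs is 899". Inputs from SAP 6: SD 0.65, correlation 0.35, two-sided alpha 0.05, conditional Prob(Width) 0.9.
- SD of the difference = 0.65 × √(2 × (1 − 0.35)) = 0.741.
- The exact conditional calculation gives 899 pairs with Prob(Width) 0.904, as stated. The other 17 rows of the table also reproduce.
- Enrolment = 899 / 0.75 = 1199.

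The match requires 0.65 to be the SD of each HbA1c measurement; read as the SD of the change, the answer would be 697 pairs. With equal SDs, the Month 6 slope of change on baseline implied by the plan is 0.35 − 1 = −0.65. No Month 3 correlation is given, so everything about the Month 3 slope below is assumed.

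**2. Bias of the common-slope model.** Let β2 and β3 be the true slopes at Months 3 and 6, and β* the fitted common slope. Let γ be the regression of Month 6 residuals on Month 3 residuals, and d the mean baseline of patients with a Month 6 value minus that of all patients. With Month 3 complete and a large sample, the Visit 3 LS mean at the all-patient mean baseline has

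bias ≈ d × [(β3 − β*) − γ(β2 − β*)].

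It is zero if the slopes are equal (then β* = β2 = β3) or if d = 0. Missingness that depends on the Month 3 value matters through the shift d that it causes.

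**3. One case by hand.** Assumed: baseline SD 0.65, β2 = −0.45, β3 = −0.65, residual correlation 0.5 (γ about 0.5), 25% missing, odds of missing doubling per SD of baseline. In the fitted data the missing and observed groups differ in mean baseline by 0.414, and β* = −0.524.
- d = −0.25 × 0.414 = −0.1035.
- Bias = −0.1035 × [−0.126 − 0.5 × 0.074] = −0.1035 × (−0.163) = 0.017 (fitted: 0.016).
- Raw observed-case mean: −0.65 × −0.1035 = 0.067 (fitted: 0.067).
- Interaction included, but LS mean taken at the baseline averaged over records: that average is shifted by 0.75 × (−0.1035) / 1.75 = −0.044, so bias = −0.65 × −0.044 = 0.029 (fitted: 0.028). The interaction alone is therefore not enough.
- Interaction included and LS mean at the all-patient mean: −0.001, which is simulation error.

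**4. Range.** ML fits with unstructured covariance. Assumed: SD 0.65 at every visit, Month 3–Month 6 correlation 0.6, odds of missing changing by a factor e per SD. Bias in percentage points of HbA1c with 40% missing at Month 6:

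| Correlation with baseline, Month 3 / Month 6 | Missingness depends on baseline | Missingness depends on Month 3 value |
|---|---|---|
| 0.35 / 0.35 | 0 | 0 |
| 0.40 / 0.35 | 0.009 | not tabulated |
| 0.50 / 0.35 | 0.028 | 0.016 |
| 0.60 / 0.35 | 0.049 | 0.034 |
| 0.50 / 0.20 | 0.063 | 0.029 |

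- At 25% missing, the last three rows give 0.015–0.04 when missingness depends on baseline and about 0.01–0.02 when it depends on the Month 3 value. The 0.40 / 0.35 row stays below 0.01.
- If, of the 40%, only 10 points depend on baseline and 30 are administrative, the last three rows fall to about 0.01–0.02.
- With an assumed baseline SD of 1.0, 25% missing and an odds ratio of 2–3 per SD, the bias is 0.017–0.031 for a slope gap of 0.15 and 0.034–0.056 for a gap of 0.30.

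**5. Direction.** If the Month 6 slope is the steeper one, loss of high-baseline patients understates the mean fall and loss of low-baseline patients overstates it. If the Month 6 slope is shallower, the signs reverse.

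**6. Coverage of the 95% interval** at the planned N = 1199, 25% missing: 90% (SD 0.65, gap 0.15, odds ratio 2), 83% (SD 1.0, gap 0.15, odds ratio 2) and 25% (SD 1.0, gap 0.30, odds ratio 3). With the interaction and the all-patient mean, coverage is about 95% in each.

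**The case against.** Several points on the other side stand.

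- **The interaction is unspecified, not excluded.** The same paragraph of SAP 8.4.2 asks for a dose trend and LS means by dose group, yet the sentence on fixed effects does not list dose. It is not a complete list of model terms.
- **Unequal slopes are an assumption.** The documents give one correlation, 0.35. That the link with baseline weakens between Month 3 and Month 6 is plausible, but they do not say so.
- **Termination does not imply selective loss.** SAP 9 attributes the missing visits to the sponsor's decision. Such a cut-off would mainly follow enrolment date, and nothing ties it to baseline HbA1c.
- **Protocol 3.1 concerns current HbA1c.** Less frequent testing follows reaching target on treatment, which points to the Month 3 value more than to baseline. That mechanism gives the smaller biases in the table.
- **The consequence is limited.** The model is an additional secondary analysis in a study without formal significance testing. Where missingness depends on baseline, the raw mean is worse: 0.07–0.10 at SD 0.65, 25% missing and an odds ratio of 2–3, against at most 0.036 for the common-slope model. That comparison covers baseline-dependent missingness only.

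A reader might infer that the bias runs up to the planned half-width of 0.05. The documents do not support that. The half-width was set for the primary paired mean at 899 pairs, and SAP 9.1 says it can no longer be reached. Nor is 0.05 a bound: some assumed inputs stay well below it and others exceed it.

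None of this is a reason to keep a common slope. It limits the size and severity of the point.

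**Conclusion.** The point holds as a conditional one. As written, the model can give a biased Visit 3 LS mean, but only when the Month 3 and Month 6 slopes on baseline differ and Month 6 missingness depends on baseline HbA1c or on the Month 3 value. Selective missingness alone is not enough.

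Under the assumed inputs of step 4, the size is about 0.00–0.04 percentage points at the planned 25% missing and about 0.00–0.06 at 40%. A wider baseline SD makes it larger; a large administrative share makes it smaller. These figures illustrate the risk and cannot be derived from the documents. The coverage figures are for 1199 patients; in the smaller terminated study the same bias is a smaller part of a wider interval.

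Severity is low to moderate: the analysis is secondary, the primary endpoint is summarised descriptively, and the remedy costs almost nothing.

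**What to change.** In SAP 8.4.2:
1. Add the baseline HbA1c-by-visit interaction to the fixed effects of the HbA1c MMRM.
2. State that the Visit 3 LS mean is computed at the mean baseline HbA1c of all patients in the analysis, counting each patient once and not averaging over visit records.

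Both parts are needed. At SD 0.65 and 25% missing, the interaction evaluated at the record average still leaves about 0.02–0.04.

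The cost is one degree of freedom and SAP wording. The SE rose from about 0.031 to 0.032, roughly 3–4%, in simulations with 600 patients and 40% missing. At N = 1199 it was 0.0198 with or without the interaction at 25% missing (SD 0.65, gap 0.15, odds ratio 2).
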